#### **6.3.1 Summaries for non-AEDs**

The number and percentage of subjects taking non-AED medications prior to first iv BRV and concomitantly with iv BRV will be summarized separately overall, and by anatomical main group (Anatomical Therapeutic Chemical [ATC] classification level 1), therapeutic subgroup (ATC classification level 2), and preferred drug name for the SS-iv. Subjects reporting multiple medications within an ATC class are counted once per medication and class.

#### **6.3.2 Summaries for AEDs**

The number and percentage of subjects taking AED medications prior to first iv BRV and concomitantly with iv BRV will be summarized separately overall, and by WHODD preferred drug name for the SS-iv.

## **7 MEASUREMENTS OF TREATMENT COMPLIANCE**

Information reported on the eCRF drug accountability (iv formulation) will be listed. The data from the eCRF Drug Accountability (oral solution and tablets) will also be listed. No summaries of drug accountability are planned.

BRV iv and oral dosing compliance will be evaluated through the review of important protocol deviations.

## 8 EFFICACY

This section is not applicable for this study.

## 9 PHARMACOKINETICS

### 9.1 Pharmacokinetics

Plasma concentration of BRV (parent compound only) before, during and after iv BRV administration will be summarized and listed for the PK-PPS.

Descriptive statistics will be calculated for each timepoint by infusion duration, visit and age cohort. These statistics will also be repeated by visit and weight group (<50 kg, ≥50 kg) and by visit and subject group (OLB, RxB and IOB combined, and IIB separately). Descriptive statistics will include: the number of observed values, geometric mean, 95% confidence interval for geometric mean, geometric CV, mean, SD, median, minimum value and maximum value. Values below LOQ will be set to LOQ for all calculations.

Box plots of plasma concentration of BRV at each timepoint (15 minutes and 3 hours) will be produced for each age cohort by visit. Infusion duration will be marked using different symbols.

Box plots of plasma concentration of BRV at each timepoint (15 minutes and 3 hours) will be produced for each infusion duration by visit. Age groups will be marked using different symbols.

A listing for plasma sample collection times and concentrations of BRV will be provided.

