## 3 DATA ANALYSIS CONSIDERATIONS

### 3.1 General presentation of summaries and analyses

Statistical analysis and generation of tables, figures, subject data listings, and statistical output will be carried out using SAS Version 9.3 or higher. All summaries will be descriptive; no statistical hypothesis testing is planned. All tables and listings will use Courier New font size 9.

Tables, figures and listings (TFL) will be displayed for the defined analysis sets. If the Safety Set (SS) and the Safety Set-iv (SS-iv) consist of the same number of subjects, TFLs will only be presented for the SS-iv.

For categorical parameters, the number and percentage of subjects in each category will be presented. The denominator for percentages will be based on the number of subjects appropriate for the purpose of the analysis. Unless otherwise noted, all percentages will be displayed to 1 decimal place. No percentage will be displayed for zero counts, and no decimal will be presented when the percentage is 100%.

For continuous parameters, descriptive statistics will include number of subjects (n), mean, standard deviation (SD), median, minimum, and maximum, unless otherwise stated.

Decimal places for descriptive statistics will always apply the following rules unless otherwise stated:

- “n” will be an integer
- Mean, SD, geometric mean, and median will use 1 additional decimal place compared to the original data
- CV [%] will be presented with 1 decimal place
- Minimum and maximum will have the same number of decimal places as the original value

However, the maximum number of decimals displayed will not exceed 4.

All summaries, unless otherwise stated, will be presented overall for all subjects, by age cohorts (Cohort 1:  $\geq 12$  to  $< 16$  years, Cohort 2:  $\geq 6$  years to  $< 12$  years, Cohort 3:  $\geq 2$  to  $< 6$  years, Cohort 4:  $\geq 1$  month to  $< 2$  years), and by infusion duration (15-minute iv infusion and iv bolus (up to 2-minute infusion)). Selected tables will be provided in addition by subject groups (OLB, RxB and IOB combined, and IIB), or by scheduled assessment timepoints as defined in [Section 4.8](#).

Selected summaries will be repeated by the country of enrollment (Hungary and rest of the World).

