### 13.3 Changes in SAP from final version 3.0 to final version 4.0

- [Section 2.3](#): Removed “application” for better wording in following sentence: “Oral BRV application can be applied during EP0065 but will not considered as study medication for EP0065”
- [Section 3.2.3](#): Concomitant medications relative time excluded from this section as unable to derive as start and stop time not collected of concomitant medications.
- [Section 3.3](#): BMI formula rewritten in terms of meters rather than cm
- [Section 3.2.9](#): Added clarification on calculating time prior to AE onset, and added calculation for number of days prior to TEAE onset.
- [Section 3.10](#): Clarified that AEs will not be summarized the periods specified in the protocol, but will be summarized relative to most recent bolus/infusion start time. Slightly reworded for clarity.
- [Section 4.2.7](#): Section added to describe potential impact of COVID-19 on this study and, how information about this will be captured and used.
- [Section 4.3](#):
  - Added clarification on the difference between the sequential cohort enrollment schematic diagram between the SAP and protocol. Spilt into two sections ([Section 4.3.1](#) which discusses sequential cohort enrollment, where text some has been modified for clarity and [Section 4.3.2](#) which has added text on how analysis will be conducted twice due to COVID-19, once using all subjects aged 2 to <16 years and 1m to < 2years on 15 -minute infusion, and once using all subjects.
- [Section 5.2](#): Information added to describe how subjects with a completed COVID-19 eCRF Impact page will be assessed, and displayed.
- [Section 6.3](#) Clarification added to describe how prior concomitant medications will be listed only if they finish 2 weeks or more prior to screening.
- [Section 9.1](#): Text added to text to explain that PK summary tables will also be produced by infusion duration. Clarification added to explain that the summary tables will be produced by the combination of OLB, RxB and IOB groups, and separately for the IIB group.
- [Section 10.1](#): Additional text added to explain the groups that the exposure table will be presented by (all subjects, infusion duration and weight).
- [Section 10.2](#): Described how an AE occurring after first dose in N1266 but prior to TC-1 will be reported in both studies.
- [Section 10.2.1](#): Clarifications added for study periods and incidence definition.
- [Section 10.5.1](#):

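### SAP 9.1 plans no dose-normalised BRV concentrations although sampled iv doses may differ by subject group, and its LOQ substitution suits IIB samples before the first infusion poorly

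*SAP*

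**What the plan says.** SAP 9.1 bases its PK tables and plots on concentrations as measured. The main table is defined by "Descriptive statistics will be calculated for each timepoint by infusion duration, visit and age cohort". Two repeats follow: "These statistics will also be repeated by visit and weight group" (below 50 kg, and 50 kg or more), and "by visit and subject group (OLB, RxB and IOB combined, and IIB separately". Box plots at 15 minutes and 3 hours are drawn per age cohort, where "Infusion duration will be marked using different symbols", and per infusion duration with age marked by symbol. One rule covers low values: "Values below LOQ will be set to LOQ for all calculations".

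SAP 3.1 sets the general layout: "All summaries, unless otherwise stated, will be presented overall for all subjects, by age cohorts" and by infusion duration. It also states "All summaries will be descriptive; no statistical hypothesis testing is planned". SAP 13.3 records that "PK summary tables will also be produced by infusion duration". SAP 10.1 summarises mean iv dose in mg/kg by age group, infusion duration and weight on the SS-iv.

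Neither SAP 9.1 nor Protocol 12.3 mentions a dose-normalised concentration. Under Protocol 5.1 and Table 7-1, IIB subjects receive 1 mg/kg (50 mg at 50 kg or more). OLB, RxB and IOB subjects receive their last oral dose, mg for mg, and the dose stays fixed until PK sampling ends. Within each cohort the infusion half comes first and the bolus half follows DMC review (Protocol 5.1). Subjects are not randomised (Protocol 7.10).

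**The concern.** PK under both modes across this age range is part of the primary objective. The main table and both sets of box plots pool subjects whose sampled dose may differ by design, and who either have or lack BRV on board at the first infusion. Plotting the two modes with different symbols in one cohort panel invites a side-by-side reading. With about 6 subjects per mode in a cohort, modest differences in who was enrolled can move that contrast without any true effect of mode. The same holds for contrasts between age cohorts.

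The planned repeats help but do not adjust the concentrations:

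- The weight split separates the 50 mg cap, yet below 50 kg the pre-treated ceiling is still 2.0 to 2.5 times the IIB dose.
- The subject-group repeat isolates IIB, but still pools OLB, RxB and IOB at varying doses. SAP 9.1 does not say outright that it is split by infusion duration.
- The dose table in SAP 10.1 can reveal an imbalance but does not carry it into the PK outputs.

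The LOQ rule is a separate matter. IIB subjects have had no BRV before their first infusion, so those samples are expected to be true zeros rather than small positive values.

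**Working it through.** The plan gives no sample size calculation to reproduce. The cell size follows from its design: 4 × 12 = 48, against approximately 50 planned, and 12 / 2 = 6 per cohort-by-mode cell, so about 24 per mode.

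**1. Allowed dose contrast.** The per-dose maximum is 5 / 2 = 2.5 mg/kg for OLB and RxB and 4 / 2 = 2 mg/kg for IOB, within 200 / 2 = 100 mg. IOB and IIB share the starting dose of 2 / 2 = 1 mg/kg (Protocol 5.1, 5.3). The ratio of the OLB/RxB ceiling to the IIB dose at weight w kg is min(2.5w, 100) / min(w, 50):

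- 2.5 up to 40 kg
- 2.22 at 45 kg
- 2.04 at 49 kg
- 2.0 from 50 kg

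**2. Shift from dose mix alone.** Assume identical, dose-proportional PK. If pre-treated subjects receive d times the IIB dose and two cells of 6 differ by k IIB subjects, the geometric mean ratio is d^(k/6).

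| k of 6 | d = 1 | d = 1.5 | d = 2 | d = 2.5 |
|---|---|---|---|---|
| 1 | 1.00 | 1.07 | 1.12 | 1.16 |
| 2 | 1.00 | 1.14 | 1.26 | 1.36 |
| 3 | 1.00 | 1.22 | 1.41 | 1.58 |

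Applying d = 2.5 to every pre-treated subject is an upper bound. If half of them are at the IOB start and half at 2 mg/kg, the effective d is √(1 × 2) = 1.41, and k = 2 gives 1.41^(2/6) = 1.12.

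**3. Chance of such an imbalance.** The documents do not give the group mix, so assume an IIB share of 10, 20 or 50%. With independent Bin(n, p) counts in the two halves:

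| Difference in IIB count | 10% | 20% | 50% | Ratio for d = 1.5 to 2.5 |
|---|---|---|---|---|
| ≥ 2 of 6 | 13% | 27% | 39% | 1.14–1.36 at k = 2 |
| ≥ 3 of 6 | 2% | 7% | 15% | 1.22–1.58 at k = 3 |
| ≥ 4 of 24 | 9% | 20% | 31% | 1.07–1.16 at 4 |
| ≥ 8 of 24 | 0.04% | 0.7% | 2.9% | 1.14–1.36 at 8 |

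The last two rows apply to the by-mode plots, which pool the cohorts. Large chance distortion there is unlikely.

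**4. Width of the planned interval.** The 95% CI factor for a geometric mean of 6 is exp(t × √(s²/6)), with t = 2.571 on 5 df and s² = ln(1 + CV²). At an assumed CV of 30%, s² = 0.0862 and the factor is 1.36. With 3 subjects at 1 mg/kg and 3 at 2.5 mg/kg, s² rises by 0.25 × (6/5) × (ln 2.5)² = 0.252 to 0.338, and the factor becomes 1.84.

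**5. What dose-normalising leaves.** Take an assumed half-life h of 5 to 9 h (the documents give none) and 12-hourly dosing. Steady-state accumulation is A = 1 / (1 − 2^(−12/h)) = 1.23 to 1.66. A 2-of-6 imbalance in IIB at the first infusion then gives A^(2/6) = 1.07 to 1.18 even at equal doses.

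**6. LOQ rule.**

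- If all IIB samples before the first infusion are below LOQ, every value equals LOQ, so the geometric mean is LOQ and the CV is 0%.
- In a mixed cell with 3 of 6 IIB and pre-treated troughs at K times LOQ (assumed), the predose geometric mean is K^(−3/6) of the pre-treated value: 0.32 for K = 10 and 0.10 for K = 100.
- The arithmetic mean hardly moves. Relative to using 0 it rises by k / ((6 − k)K), which is 0.2% (k = 1, K = 100) to 10% (k = 3, K = 10).
- Only predose rows at the first infusion are affected. The box plots show 15 minutes and 3 hours only.

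**The case against.** The plan delivers what the protocol asks for. The PK variable is plasma concentration, Protocol 12.3 asks for descriptive statistics of it, and no comparison of modes is tested. Raw values also answer whether levels lie in the adult range, on which dose selection rests. All of this stands, and is why the raw tables should stay.

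Much of any shift would sit within noise. For two cells of 6, the 95% CI factor for a ratio is exp(2.228 × √(s²/3)), or 1.29, 1.46 and 1.84 at assumed CVs of 20, 30 and 50%. The 2-of-6 shifts at d up to 2 fall inside even the first. This limits the importance but does not remove the shift, and at d = 2.5 the 1.36 exceeds 1.29.

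A reader might infer several stronger claims that the documents do not support:

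- *That only mode and age are used.* SAP 9.1 repeats the statistics by weight group and by subject group, with IIB apart. SAP 3.1 and 4.7 point to presentation by infusion duration too, so what remains there is a wording clarification.
- *That no LOQ rule exists for IIB predose samples.* One does; the issue is its fit to expected zeros.
- *That a 2- to 2.5-fold dose gap is typical.* Those are ceilings. IOB and IIB start at the same 1 mg/kg.
- *That younger cohorts must differ in mix.* N01266 takes direct entrants only from 4 years, but it also follows subjects from N01263, which enrolled from 1 month. A lower OLB share would not by itself mean a different dose.

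**Conclusion.** The point holds as a minor, inexpensive improvement and not as an error in the plan. SAP 9.1 has no dose-normalised summary, sampled doses may differ up to 2.5-fold, and mode is neither concurrent nor randomised. Raw contrasts by mode or age in cells of about 6 may therefore partly reflect dose mix.

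The size is conditional on a group mix and doses that the documents do not report. It is zero at equal doses or equal mix, modest and plausible within a cohort, and small in the pooled by-mode plots. All ratios assume dose proportionality and otherwise identical PK. A reader might conclude that the planned outputs will be biased, but the documents do not show that an imbalance exists.

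The LOQ rule misdescribes IIB samples before the first infusion, chiefly through the geometric statistics. The mixed-cell figures rest on an assumed ratio of trough to LOQ.

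**What to change.** In SAP 9.1:

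1. Keep the raw tables and plots. Add dose-normalised summaries and box plots (concentration divided by the mg/kg actually infused at that infusion) for the 15-minute and 3-hour samples only. Flag partial infusions: in a pre-treated subject the carry-over comes from the earlier full dose, so the normalised value is too high by the factor (f + A − 1) / (fA). That is 6 to 13% for f = 0.75 and the assumed half-life of 5 to 9 h.
2. State that the table of IIB against OLB, RxB and IOB combined is shown by infusion duration, following the SAP 3.1 default. Give IIB subjects their own symbol in the box plots.
3. For IIB samples before the first infusion, use 0 for values below LOQ in arithmetic statistics, exclude them from geometric statistics, and report n and the number below LOQ in each cell.

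The cost is a few sentences and some extra outputs. Delivered dose, infusion times and sampling times are already recorded (Protocol 7.7 and 9), so no new data are needed. There are three downsides. Dose proportionality is documented only for oral troughs. Normalising leaves the accumulation difference between IIB first doses and pre-treated subjects, which is why item 2 is needed as well. Arithmetic and geometric predose statistics will rest on different n, and in a mixed cell the geometric mean will then describe essentially the pre-treated subjects.

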### 9.2 Pharmacodynamics

This section is not applicable for this study.

## 10 SAFETY ANALYSIS

All analyses for extent of exposure and safety are performed for the SS-iv. Selected tables will be performed on the SS.

Inferential statistical tests are not planned for the safety variables.

### 10.1 Extent of exposure

The duration of iv BRV exposure, as defined in [Section 3.2.6](#), will be summarized as continuous parameters (once in hours and once in days) for the iv PK Period on the SS-iv. The number and percentage of subjects who received 0, 1, 2, 3, ..., 10 BRV infusions will be displayed for the SS-iv. Handling of missing study medication data is described in [Section 4.2.5](#). Mean iv BRV dose (mg/kg) will be summarized as continuous parameters for the iv PK Period for the SS-iv. This table will be presented by age groups for all subjects, by infusion duration and by weight (<50kg and ≥50kg).

The duration of overall oral BRV exposure, oral BRV exposure from tablets and oral BRV exposure from oral solution as defined in [Section 3.2.6](#), will be summarized as continuous parameters (in days) separately for the IOB Treatment Period and the Follow-up Period for the SS.

The overall BRV duration (oral BRV and iv BRV exposure), as defined in [Section 3.2.6](#), will be summarized as a continuous parameter (in days) for the SS-iv and SS respectively.

The following listings will be provided for the SS unless otherwise stated:

- study medication administration, which displays relevant information about the BRV iv dosing including the start and stop time of each infusion, the target dose and whether the target dose was delivered.
- BRV exposure, which displays relevant information about the BRV iv and oral dosing including the number of infusions received, and the total BRV exposure.
- Oral BRV dosing during study
- Oral BRV administration from oral solution
- Oral BRV administration from tablets

## 10.2 Adverse Events

All adverse events (AEs) occurring during EP0065 (ie, after signing of the ICF) must be reported. For subjects who transition to study N01266, any AEs which began after the first dose of BRV in N01266 but prior to TC-1 of EP0065 will be considered as during EP0065 and N01266. Pre-treatment adverse events (PTAEs) are defined as AEs that had onset strictly prior to the date/time of the first BRV medication taken during EP0065. For OLB subjects, where the AE started prior to EP0065 enrollment, information will come from the respective OLB study.

Treatment-emergent adverse events (TEAEs) are defined as those events which started on or after the first BRV medication taken during the EP0065 study. Subjects who began the study on BRV treatment (OLB and RxB subjects) will be assumed to have taken BRV treatment on the first day of screening. Timing of an AE being treatment emergent varies by subject group: all AEs are treatment emergent for RxB and OLB subjects; all AEs on or after the IOB Treatment Period are treatment emergent for IOB subjects; all AEs on or after the iv PK Period are treatment emergent for IIB subjects.

Data handling rules for management of missing or partial start or stop dates for adverse events should follow those defined in the [Section 4.2.4](#). The classification of TEAE will be done after imputation of any partial start dates.

### 10.2.1 AE summaries

All AE tables will be summarized separately over all AEs and by MedDRA SOC and MedDRA PT. The number and percentage of subjects experiencing each event at least once will be summarized. All summaries will be sorted alphabetically by SOC and by frequency of events within PTs, starting with the most frequent event overall. All summaries are for all study periods combined (Screening, IOB treatment, iv-PK, Follow-up, and Safety (BRV free) Period) unless otherwise indicated. Only the first occurrence of a TEAE of a particular PT will be included in incidence calculations, but all occurrences of TEAEs of the same PT will be included in counts of TEAEs. For summaries by study period, AEs are assigned only to the period on which they began. TEAEs of interest is a selection of TEAEs identified by UCB to be of interest to BRV.

The following summaries will be produced overall and by age cohort, for all subjects and separately by infusion duration, and subject group for the SS-iv:

- Incidence of AEs – Overview (number and percentage of subjects with at least one: AE, TEAE, serious TEAE, non-serious TEAE, TEAE of interest, TEAE requiring dose change,

drug-related TEAE, drug-related serious TEAE, and severe TEAE, as well as the number and percentage of subjects who discontinued due to a TEAE, had permanent withdrawal of BRV due to a TEAE, had an AE leading to death, and had a TEAE leading to death)

- Incidence of TEAEs
- Incidence of TEAEs Leading to Study Discontinuation
- Incidence of Serious TEAEs

The following AE summaries will be produced overall and by age cohort, for all subjects and separately by infusion duration for the SS-iv:

- Incidence of PTAEs
- Incidence of TEAEs by Maximum Intensity  
Each subject will be counted at most once per primary SOC or PT according to the maximum intensity of all AEs within that SOC or PT. Severe intensity will be assumed for AEs for which intensity is not specified.
- Incidence of TEAEs by Maximum Relationship  
Drug-related AEs are AEs for which the relationship to trial medication is specified as related or AEs for which relationship is not specified.
- Incidence of TEAEs of Interest
- Incidence of Non-serious TEAEs Occurring in at least 5% of Subjects
- Incidence of Serious TEAEs by Relationship to BRV
- Incidence of Fatal TEAEs by Relationship to BRV

The following summaries will also be produced by country of enrollment (Hungary and rest of the World) for all subjects, by infusion duration and by subject group for the SS-iv:

- Incidence of AEs – Overview
- Incidence of TEAEs

The following summary will also be produced by country of enrollment (Hungary and rest of the World) for all subjects and by infusion duration for the SS-iv:

- Incidence of TEAEs by Maximum Intensity

The following summaries will be produced overall and by age cohort and study period, for all subjects and separately by infusion duration and subject group for the SS:

- Incidence of TEAEs by Study Period
- Incidence of TEAEs Leading to Study Discontinuation by Study Period
- Incidence of Serious TEAEs by Study Period

The following summaries will be produced overall and by age cohort and study period, for all subjects and by infusion duration for the SS:

- Incidence of TEAEs by Maximum Intensity by Study Period

- Incidence of TEAEs by Maximum Relationship by Study Period

The following TEAE summaries will be produced overall and by age cohort for the SS:

- Incidence of Serious TEAEs - Subject Numbers
- Incidence of TEAEs Leading to Study Discontinuation - Subject Numbers

Additionally, incidence of TEAEs will be summarized by categorized relative time infusion for all subjects, and by age cohort for the SS-iv. The time of each AE relative to the start of the previous iv infusion will be calculated as described in [Section 3.2.4](#) and categorized into 0- $\leq$ 5 minutes,  $>5 - \leq 15$  minutes,  $>15$  to  $\leq 60$  minutes,  $>60 - \leq 12$  hours and  $>12$  hours.

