The OLB subjects will temporarily discontinue assessments in their long-term, open-label study when they enter EP0065. As such, all assessments for these subjects during the Screening Period (and subsequent periods of EP0065) will be recorded in the EP0065 Case Report form (CRF) until they return to a long-term, open-label study or discontinue BRV treatment.

IOB Treatment Period (2 to 10 days of oral BRV treatment; for IOB subjects only)

Only IOB subjects who meet all eligibility criteria may participate in the IOB Treatment Period. No other subjects may participate in this period.

During the IOB Treatment Period, IOB subjects will initiate treatment with oral BRV 2mg/kg/day not to exceed 100mg/day for subjects with body weights ≥ 50 kg and must have, at minimum, 2 days of treatment with oral BRV before entry into the iv PK Period. Subjects who do not enter the iv PK Period will not be eligible for the long-term, open-label study.

The Investigator is permitted to adjust the oral BRV dose during the IOB Treatment Period in accordance with medical judgment (with a maximum dose of 4mg/kg/day, not to exceed 200mg/day for subjects with body weights ≥ 50 kg); however, subjects must have no change in the oral BRV dose for the 2 days prior to entry into the iv PK Period.

iv PK Period (1 to 6 days, with Day 1 defined as the initial day of iv BRV infusion)

[figure not shown]
During the iv PK Period, iv BRV will be administered every 12 hours ± 2 hours (q12h ± 2 h). All subjects are to receive 1 to 2 consecutive doses of BRV; however, based on medical need, subjects may receive up to 10 consecutive doses of iv BRV. The PK sampling will occur with the first iv BRV administration and with 1 other iv BRV administration.

The first dose of iv BRV will be as follows:

- OLB, RxB, and IOB subjects: mg-to-mg equivalent of the oral BRV dose immediately prior to the iv PK Period; administered q12h ± 2 h after prior oral dose
- IIB subjects: 1mg/kg not to exceed a maximum of 50mg for subjects ≥ 50 kg

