### 2.3 Study design and conduct

EP0065 is a Phase 2 multicenter, open-label study to evaluate the PK, safety, and tolerability of iv BRV administered as a 15-minute iv infusion and an iv bolus (up to 2-minute infusion) in subjects  $\geq 1$  month to  $< 16$  years of age with epilepsy.

Study medication is defined by iv infusion of BRV administered as a 15-minute iv infusion or an iv bolus (up to 2-minute infusion). Oral BRV can be administered during EP0065 but will not be considered as study medication for EP0065.

Approximately 50 enrolled subjects will receive iv BRV in the following age-based cohorts (approximately 12 subjects/cohort):

- Cohort 1:  $\geq 12$  to  $< 16$  years
- Cohort 2:  $\geq 6$  years to  $< 12$  years
- Cohort 3:  $\geq 2$  to  $< 6$  years
- Cohort 4:  $\geq 1$  month to  $< 2$  years

The age at Screening Visit will be the determining factor for age cohort assignment. Each age cohort will have approximately 50% of subjects with iv BRV infusion and 50% with bolus BRV.

The following subjects will be eligible for enrollment in EP0065:

- Open-label BRV (OLB) subjects: currently receiving oral BRV as participants in a long-term, open-label study
- Prescribed BRV (RxB) subjects: currently receiving prescribed oral BRV from commercial supply
- Initiating Oral BRV (IOB) subjects: not currently receiving BRV; first dose of BRV in EP0065 will be oral tablet or solution
- Initiating iv BRV (IIB) subjects: not currently receiving BRV; first dose of BRV in EP0065 will be by iv Infusion

For OLB and RxB subjects, the maximum BRV dose is 5mg/kg/day (rounded). For IOB and IIB subjects, the maximum BRV dose is 4mg/kg/day. Throughout the study, no subject may receive a dose greater than BRV 200mg/day. Subjects will receive oral BRV (tablets or oral solution) in equally divided doses; BRV oral solution may be given by enteric administration (eg, by feeding tube) based on subject need.

The EP0065 study periods and visits are described below. The PK assessments will be made during the iv PK Period only and safety data will be collected throughout the study, with intensive collection of safety data with each iv BRV dose administered. A Schedule of Study Assessments is provided in the protocol for the Screening through iv PK Periods and for the Down-Titration Period and Safety (BRV-free) Periods (for subjects not continuing BRV).

- Screening Period (1 to 10 days)

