During the Screening Period, the OLB and RxB subjects will continue treatment with oral BRV using their assigned open-label study supply or prescribed commercial supply, respectively. The IOB and IIB subjects will not receive BRV during this period.

The OLB subjects will temporarily discontinue assessments in their long-term, open-label study when they enter EP0065. As such, all assessments for these subjects during the Screening Period (and subsequent periods of EP0065) will be recorded in the EP0065 Case Report form (CRF) until they return to a long-term, open-label study or discontinue BRV treatment.

- IOB Treatment Period (2 to 10 days of oral BRV treatment; for IOB subjects only)

Only IOB subjects who meet all eligibility criteria may participate in the IOB Treatment Period. No other subjects may participate in this period.

During the IOB Treatment Period, IOB subjects will initiate treatment with oral BRV 2mg/kg/day not to exceed 100mg/day for subjects with body weights  $\geq 50$ kg and must have, at minimum, 2 days of treatment with oral BRV before entry into the iv PK Period. Subjects who do not enter the iv PK Period will not be eligible for the long-term, open-label study.

The Investigator is permitted to adjust the oral BRV dose during the IOB Treatment Period in accordance with medical judgment (with a maximum dose of 4mg/kg/day, not to exceed 200mg/day for subjects with body weights  $\geq 50$ kg); however, subjects must have no change in the oral BRV dose for the 2 days prior to entry into the iv PK Period.

- iv PK Period (1 to 6 days, with Day 1 defined as the initial day of iv BRV infusion)

During the iv PK Period, iv BRV will be administered every 12 hours  $\pm 2$  hours (q12h  $\pm 2$ h). All subjects are to receive 1 to 2 consecutive doses of BRV; however, based on medical need, subjects may receive up to 10 consecutive doses of iv BRV. The PK sampling will occur with the first iv BRV administration and with 1 other iv BRV administration.

The first dose of iv BRV will be as follows:

- OLB, RxB, and IOB subjects: mg-to-mg equivalent of the oral BRV dose immediately prior to the iv PK Period; administered q12h  $\pm 2$ h after prior oral dose
- IIB subjects: 1mg/kg not to exceed a maximum of 50mg for subjects  $\geq 50$ kg

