## 2.4 Determination of sample size

The primary objective of the study is to evaluate the PK, safety, and tolerability of BRV given intravenously. The plan for approximately 50 enrolled subjects (4 age cohorts of approximately 12 subjects each) to receive iv BRV was deemed clinically appropriate for the evaluation of the PK, safety, and tolerability of iv BRV administration in subjects  $\geq 1$  month to  $< 16$  years of age with epilepsy. No formal sample size calculation has been performed.

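### TEAE percentages by infusion duration take no account of how many infusions each child received (1 to 10); a first-infusion table by mode would largely remove the problem

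*SAP*

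**What the plan says.** SAP 10.2.1 defines the metric for the adverse event tables: "The number and percentage of subjects experiencing each event at least once will be summarized". For the overview and the main TEAE tables the layout is: "The following summaries will be produced overall and by age cohort, for all subjects and separately by infusion duration, and subject group for the SS-iv". By default the tables pool the whole study ("All summaries are for all study periods combined", with exceptions allowed). The exceptions include TEAEs by study period on the SS, also split by infusion duration. All occurrences of a TEAE are counted as well as the children affected.

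Exposure is set in SAP 2.3: "All subjects are to receive 1 to 2 consecutive doses of BRV", but "based on medical need, subjects may receive up to 10 consecutive doses of iv BRV". Protocol 5.1 says the same. The size of each group follows from SAP 2.4 ("4 age cohorts of approximately 12 subjects each") and SAP 2.3 ("Each age cohort will have approximately 50% of subjects with iv BRV infusion and 50% with bolus BRV"). Protocol 7.10 states that subjects are not randomized, and in each age cohort the 15-minute half is enrolled before the bolus half (SAP 2.3).

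Other planned displays bear on this point:
- SAP 10.1 tabulates how many children had 0, 1, 2 and so on up to 10 infusions, with the exposure table also by infusion duration. It lists the start and stop time of each infusion.
- SAP 10.2.1 tabulates TEAEs by time since the start of the previous infusion, for all subjects and by age cohort. Infusion duration is not named for that table.
- SAP 3.1 states that all summaries are descriptive, with no hypothesis test.

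**The concern.** The primary objective covers the tolerability of BRV given in two ways, and adverse events are a primary safety variable. A reader of the report will look at the 15-minute and bolus columns side by side. The percentage in each column depends on the risk at each administration and on how many administrations each child had. The second is driven by medical need, and nothing in the design balances it between modes. In a small cell, one or two children with long courses could make a mode look worse, or could mask a real difference. The adverse event table itself would not show that this had happened. No adverse event table by infusion duration either gives each child the same number of opportunities or divides by the number of infusions.

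**Working it through.** **Group sizes.** 4 cohorts × 12 = 48, which agrees with the planned total of about 50. Half of 12 is 6 children per age-by-duration cell, and 4 × 6 = 24 per duration. The plan has no power or alpha figure to reproduce.

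**Children with at least one event.** Let p be the chance of a TEAE per infusion. The documents give no value, so I assume 0.02 to 0.20, the same for both modes and independent between infusions. After k infusions the chance of at least one event is 1 − (1 − p)^k. For p = 0.05: 1 − 0.95 = 5.0% for k = 1; 1 − 0.95² = 9.8% for k = 2; 1 − 0.95¹⁰ = 40.1% for k = 10.

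**Spurious difference between two cells of 6.** Average that formula over the infusion counts in each cell and subtract. The infusion mixes are assumed. Results are in percentage points:

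| Infusion counts in the two cells | p=0.02 | p=0.05 | p=0.10 | p=0.20 |
|---|---|---|---|---|
| three on 1 and three on 2, vs all on 2 | 1.0 | 2.4 | 4.5 | 8.0 |
| all on 1 vs all on 2 | 2.0 | 4.7 | 9.0 | 16.0 |
| all on 2 vs one of six on 10 | 2.4 | 5.1 | 7.7 | 8.9 |
| all on 2 vs two of six on 10 | 4.8 | 10.1 | 15.4 | 17.8 |
| all on 2 vs all on 10 (extreme) | 14.3 | 30.4 | 46.1 | 53.3 |

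For example, one child of six on 10 infusions at p = 0.05: (40.1 − 9.8)/6 = 5.1 points. If each child contributes only the first infusion, the expected value is p in both cells and the spurious difference is 0.

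**Chance variation, for scale.** The SD of a difference between two groups of n is √(2π(1 − π)/n), where π is the incidence. With n = 6 and π = 10% to 40% this is 17 to 28 points. With n = 24 it is 9 to 14 points. Exact 95% limits for 1 of 6 are 0.4% to 64.1%.

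**Do the by-period tables remove it?** SAP 3.2.5 runs the iv PK Period from the first infusion to 12 h after the start of the last. One infusion gives a window of 12 h. Ten at exactly 12-hour intervals give 9 × 12 + 12 = 120 h. These tables take out screening, oral and down-titration time, but the window still lengthens with each infusion.

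**The case against.** The strongest reply is that the plan already shows most of what is needed.
- It makes no formal comparison: the tables are descriptive and no contrast is defined.
- The by-period tables isolate the iv PK Period by infusion duration.
- The exposure table would reveal an imbalance in infusions. Event counts and listings would let a reader approximate a rate or pick out first-infusion events.
- SAP 3.1 makes the split by infusion duration a default, so the time-since-infusion table might be read as including it.
- One or two doses are the norm, and with these cell sizes chance outweighs any plausible artefact.

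Much of this stands. A reader might infer that the bolus-versus-infusion difference will reflect how many infusions were given. The documents do not support that: they give no reason why long courses should fall more in one mode.

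A reader might also infer that unequal follow-up distorts the comparison, since TEAE observation can run to 10 + 6 + 28 + 14 = 58 days with down-titration. The by-period tables answer most of that, and its length turns on subject group and down-titration rather than on mode.

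Four things are left. The exposure table shows an imbalance without removing it. Event counts are numerators that also rise with infusions. The time-since-infusion table states its own strata, which do not include infusion duration, and it pools all infusions of a child. Rebuilding a first-infusion comparison from listings is work the analysis should do. Small numbers are plain to any reader, but an exposure artefact is not visible in an adverse event table.

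**Conclusion.** The point holds as a possibility, not as a prediction. TEAE percentages by infusion duration can be confounded by the number of infusions, and no planned adverse event table by mode removes this. If cells differ only by 1 versus 2 infusions, the artefact is about 1 to 16 points over the assumed risks. With one or two children of six on 10 infusions against none, it is about 2 to 18 points. It becomes large only if many children in one mode have long courses. In cells of 6 it is generally below one SD of chance variation. With 24 per mode and the same mixes in every cohort, it can approach or exceed that SD. These figures rest on an assumed risk per infusion, equal in both modes and independent between infusions, and on illustrative infusion counts. This is an inexpensive improvement to a descriptive analysis, not a defect that undermines the plan.

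**What to change.** In SAP 10.2.1, on the SS-iv:
1. Add a table of the incidence of TEAEs that start after the start of the first infusion, within 12 h and before any second infusion. Present it by infusion duration, overall and by age cohort. Each child then has about one equal opportunity (dosing every 12 h ± 2 h makes the window 10 to 12 h), and the result does not depend on whether a child stops after an event.
2. State that the table by time since the previous infusion is also presented by infusion duration.
3. State that these two displays are the main descriptive basis for any remark on 15-minute infusion versus bolus tolerability.

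TEAEs per 100 infusions may be shown as supportive only, with a note that the rate includes repeat events within a child, is still driven by children with long courses, and assumes constant risk per infusion. The SAP should also say how an event with no recorded onset time on the day of the first infusion is handled in the new table, because the imputation in SAP 4.2.4 is limited to treatment-emergent classification.

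The cost is one extra table and one extra split, from infusion and onset times already recorded. The limitation is that first-infusion results say nothing about repeated dosing, so the planned tables should stay.
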